Figure 5: Portable freezer/Cold Box for ease of transportation of samples to MPL and frozen samples to TFNC.

Items to be taken to the field for EACH survey teams. Complete list of supplies to be taken by each team for specimen collection of 21 women is given in Annexure 3 **Specimen processing and storage at MPL:**

Kindly ensure ACCURATE LABELLING of all samples.

After the samples are brought to the NPL, one of the EDTA vacutainers will be tested for automated blood cell counts in the Automated Blood Cell Counter. Any subject found to be anemic will be tested for the manual reticulocyte count.

The second EDTA tube will be used for red cell folate analysis for which 100 \Box 1 EDTA blood will be transferred after gently mixing to two plastic cryovials which contains 1 ml of 1% ascorbic acid solution. The pipette tip will be rinsed a few times in the ascorbic acid solution to ensure quantitative transfer of the EDTA blood. It is critical that the pipetting is done accurately. This vial should be labeled and stored at -20°C.

The leftover sample will be spun for plasma separation at low speed and plasma will be transferred in two cryovials for plasma homocysteine. Samples will be stored at -20° C at NPL.

Note: At room temperature there is an increase in HCY of about 10% per hour! Therefore it should be ensured that the sample processing is performed as soon as possible.

For serum separation, the clotted blood sample will be centrifuged at 1000 g for 10 minutes. Serum will be aliquoted ($300\square1$ each) into four plastic cryovials and one PCR vial: for Vitamin B12, retinol, folate and a backup vial. PCR vial for [name] (Germany) needs and aliquot of ~100 ul serum for ferritin, sTfR, CRP, AGP, and RBP.

Samples	Biomarker	Storage Conditions
K ₂ EDTA 1 st vacutainer	Hemoglobin	4ºC
	Reticulocyte count (if necessary)	
	DNA extraction for MTHFR	
K ₂ EDTA 2 nd vacutainer	1. RBC folate	-20°C
	2. Back up for whole blood folate	
	3. Plasma for homocysteine	
	4. Back – up vial for Plasma	
Yellow capped vacutainer	1. Serum folate	-20°C
	2. Serum B 12	
	3. Serum Retinol	
	4. Serum backup	
	5. Serum Fe, sTfR, CRP, AGP, and	
	RBP	

Table 3: Shows details of sample collection, parameters to be tested and storage conditions at NPL

Note: All samples for tests to be performed in batches on frozen samples will be transferred to -70° C deep freezers after the samples reach TFNC.

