One lab tech will be assigned to run the hematology analyzer using purple top vacutainer#1 and the leftover sample will be refrigerated in the same vacutainer and transported to PGIMER. (Figure 10)

[figure not shown]
Two lab techs will be assigned to make whole blood lysates (see SOP for making lysates) first and then centrifuge the leftover sample for plasma. Aliquots will be made as shown below. (Figure 11)

Purple Top #2 –Vacutainer – makelysates and centrifuge the rest for plasma. Aliquot into 4 cryovials

The fourth lab tech will centrifuge the yellow top vacutainer for serum and aliquot into 6 cryovials as shown below (Figure 12)

Yellow Top Vacutainer – centrifuge for serum and aliquot into 6 cryovials

After placing the samples in appropriate boxes, lab techs will place a check mark in appropriate places in the transmittal form. The boxes will have to be manually numbered and the box number has to be recorded in the transmittal form.

The leftover samples in one purple top vacutainer and the yellow top vacutainer should be kept refrigerated in a large Ziploc bag and transported to PGIMER.

13 Sorting Cryovials into Cryovial Boxes

[figure not shown]
Cryovials must be sorted properly into cryovial boxes according to specimen type. This is essential to ensure the correct specimens are shipped to the correct laboratory for processing. Laboratory Technicians are responsible for sorting the cryovials into the correct cryovial boxes according to specimen type during the processing of specimens. Once the Hematology is completed, the lab tech will place the purple vac #1 in the fridge and place a check mark in the transmittal form.

All cryovials need to be sorted in the following order. Also see Figure 8.

- Serum Folate and Vitamin B12 will be arranged in one box.
- Serum Ferritin and sTfR in one box
- Serum CRP and extra serum vials in one box. 0
- WBL Folate and WBL Extra in one box. 0
- Plasma Homocysteine and Extra plasma vial in one box.

A total of 5 cryovial boxes will be transported in the portable freezer, and 1 Vacutainer rack will be transported in the cold box to PGIMER every 2 days.

Figure 13: Sorting of cryovials in boxes.

Box samples by test, store boxes at -20°C till transporting to PGIMER lab (twice a week)

14 Transportation of Specimens from MPL to TFNC Lab

Every 2 days (cold chain logistics):

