Vacutainers	and the frozen gel packs so that they do not touch. There will be 2 purple
	top vacutainers and one yellow top vacutainer. All the specimens in the cold
	box and the portable freezer must be sent at the end of the day for
	processing and storage.
	The Lab Technicians should keep the cold box closed at all times. Avoid
	leaving the lid open and exposure to direct sun. A digital thermometer will
Cold Boxes	be included in each cold box. The temperature of the cold box should
	remain $<8^{\circ}$ C. When temperature of the cold box reaches $\sim6^{\circ}$ C call the
	Supervisor to have a Driver deliver new frozen gel packs.
	The purple top vacutainer #1 for measuring: 1) Hemoglobin/CBC using the
Purple Top	automated hematology analyzer at MPL 2) Reticulocyte count at MPL if
Vacutainer#1	necessary. 3) DNA extraction for MTHFR. Extracted DNA will be stored in
	labeled Eppendorf tubes after completing the extraction procedure.
Purple Top	The purple top vacutainer #2 will be used to make 1) WBL for the Folate
Vacutainer#2	microbiological assay 2) Backup of WBL. Then the vacutainer will be spun

17 Annexure 2: Cold Chain Logistics

	down in the centrifuge for 3) Plasma HCY 4) Back up vial for Plasma.
Yellow Top Vacutainer	The yellow top vacutainer needs to be spun down for serum using the centrifuge and then aliquoted into 4 cryovials and 1 PCR vial for 1) Serum Folate, 2) Serum B12, 3) Serum Retinol, 4) Back-up vial for serum, 5) PCR vial for Ferritin, sTfR, CRP, AGP, RBP

19 Four teams will collect 21 samples from each village, $n = 21$						
	21 households per village (plus extra supplies)					
Supply Item	Quantity Required					
Backpack	4					
Yellow Top Vacutainers	25 per team= 50 per day					
Purple Top Vacutainers	50 per team= 100 per day					
Tourniquet	2 per team= 4 (can be reused)					
21G Needles	25 per team= 50 per day					
Vacutainer Barrels	4 per team (can be reused)					
Sharps container	1 Box each= 2					
Alcohol pads	30 per team= 60 per day					
Gauze pads	30 per team= 60 per day					
Absorbent pads	2 (can be reused if clean)					
Biohazard bags	2					
Ziploc bags	15 small per team= 30 per day					
Labels	3 sets pre-printed per subject= 25 sets					
Cold box	1 per team= 2					
Frozen Gel Packs	4-5 for each cold box= 10					
Bubble Wrap	2Large Piece (to protect specimens from frozen gel packs inside each cold box)					
	1 each for cold box $=2$					
Digital Thermometer						
Vacutainer Rack for						
Cold Box	1 each per box					

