- 1. Return to the laboratory promptly. Ideally, the whole blood should be lysed the same day as it was collected. However, if that is not possible, maintain the EDTA Vacutainer tube in the refrigerator protected from light for up to a maximum of 2 days before lysis.
- 2. When you are ready to lyse the whole blood, remove one vial with ascorbic acid diluent per subject from the laboratory freezer and allow it to thaw at room temperature.
- 3. Alternatively, prepare fresh 1% ascorbic acid solution and accurately pipet 1 mL into a 2mL cryovial. Allow the EDTA Vacutainer to reach room temperature and re-mix its contents by inversion at least 8-10 times.
- 4. Remove the stopper of the EDTA Vacutainer and pipet 100 μ L of well-mixed blood into the vial containing the ascorbic acid; mix well.
- 5. Determine the hematocrit by using a portion of the remainder EDTA whole blood.
- 6. If EDTA plasma is needed for analysis, re-stopper the EDTA Vacutainer carefully and centrifuge it for 10 minutes at 2500-2800 RPM to separate the plasma from the cells.
- 7. If not, discard the EDTA Vacutainer properly in accordance with hospital regulations.

III. Storage:

- 1. Place all RBF samples (lysed whole blood) in white 9x9 array cardboard storage boxes labeled appropriately for study, and freeze all samples at -70°C.
- 2. When filling the box, mark the top left corner with a marker pen to indicate starting point.
- 3. Continue to fill each row, left to right, until box is completely filled.
- 4. As patient samples are collected and processed, create a logsheet for each box listing the subject id, date collected, location of the vials in the box, and any pertinent information

which may affect assay results such as short draw, fasting status if known, hemolysis, lipemia, etc. - and the patient hematocrit result for correct calculation of the RBF.

IV. Transport:

- 1. Wrap the pre-labeled white storage box with absorbent paper, place it into a Ziplock bag and seal the bag.
- 2. Place the Ziplock bag in the bottom of the shipping box. If necessary, use sheets of bubble wrap to ensure specimens remain in a vertical position.
- 3. Fill the Styrofoam-lined shipping box with dry ice. Allow one pound of dry ice for every 2 hours in transport.
- 4. Close the Styrofoam lid.
- 5. Place a copy of the study logsheet describing these samples between this lid and the outer cardboard lid.
- 6. Seal the outer carton lid.

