- 1. Ideally, the whole blood should be lysed the same day as it was collected. However, if that is not possible, the EDTA Vacutainer tube may be kept in the refrigerator of- (2°C-8°C) protected from light for a maximum of 4 days before lysis.
- 2. When ready to lyse the whole blood, prepare 1% ascorbic acid diluent as described. Weigh 5g of ascorbic acid dissolve in 500ml of autoclaved distilled water.
- 3. Transfer the ascorbic acid in 1ml vials and store in a refrigerator of -20°C.

Note: it should be freshly prepared each day of lysing.

Procedures for lysing a whole blood sample.

- 1. Allow the EDTA Vacutainer to reach room temperature and re-mix its contents by inversion at least 8–10 times.
- Remove the stopper of the EDTA Vacutainer and pipet 100 μL of well-mixed blood into thawed 1ml tube of ascorbic acid (1 g/dL) solution (rinse the pipette tip 3–4 times with the RBC hemolysate), then mix well (avoid foaming) and allow to stand in the dark 30 min at room temperature.

Storage:

[figure not shown]
- 1. Place all RBF samples (lysed whole blood) in white 9x9 array cardboard storage boxes labeled appropriately for the study, and freeze all samples at -70°C.
- 2. When filling the box, mark the top left corner with a marker pen to indicate starting point. Continue to fill each row, left to right, until box is completely filled.

3. As household samples are collected and processed, create a log sheet for each box listing the following, the household ID, date collected, location of the vials in the box, and any information that may affect assay results, such as short draw, fasting status if known, hemolysis, or lipemia, and the household hematocrit result for correct calculation of the RBF.

I have read, understood and agreed to follow the procedure as documented

No.	Name	Signature	Date

Standard Operating Procedure (SOP) for Sample Separation, aliquoting and Storage

TANZANIA FOOD AND NUTRITION CENTRE

Version No:		Copy no.	
Prepared by:			
Reviewed by:	1. 2.		
Authorized by:			

Changes:

 	• • • • • • • • • • • • • • • • • • • •

Reasons for changes:

• • • • • • • • • • • • • • • • • • • •			•••••••••••••••••••••••••••••••••••••••
• • • • • • • • • • • • • • • • • • • •	•••••••••••••••••	•••	

SCOPE

Procedure for sample separation, aliquoting and storage for the survey tittled: Morogoro Regional Micronutrient Household and Biomarker Survey, Tanzania, 2019.

PURPOSE

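### The EDTA tube used for homocysteine is brought to room temperature for the folate lysate before its plasma is spun, so homocysteine may be biased upward by an amount the protocol does not fix

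*Protocol*

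**What the plan says.** Section 8.3 (specimen processing and storage at MPL, with its Table 3) gives EDTA tube 2 two jobs: the red-cell folate lysate and the homocysteine plasma. Annexure 2 repeats this: "The purple top vacutainer #2 will be used to make 1) WBL for the Folate" assay, then a backup lysate, then plasma for homocysteine.

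The order of work is explicit. Two technicians are to "make whole blood lysates (see SOP for making lysates) first and then centrifuge the leftover sample for plasma". The processing text agrees, lysate first and then: "The leftover sample will be spun for plasma separation at low speed and plasma will be transferred in two cryovials for plasma homocysteine".

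The SOP for lysing whole blood begins the lysing procedure with "Allow the EDTA Vacutainer to reach room temperature and re-mix its contents by inversion". The SOP for RBC and serum folate collection and processing has the same step before pipetting ("Allow the EDTA Vacutainer to reach room temperature and re-mix its contents by inversion at least 8-10 times"). Plasma comes only later in that SOP: "If EDTA plasma is needed for analysis, re-stopper the EDTA Vacutainer carefully and centrifuge it for 10 minutes".

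Directly after the instruction to spin for homocysteine, section 8.3 warns: "At room temperature there is an increase in HCY of about 10% per hour". It continues: "Therefore it should be ensured that the sample processing is performed as soon as possible". It gives no limit in minutes, no cold spin and no correction.

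The SOP for sample separation, aliquoting and storage describes a different flow. The blood count, the 100 µL lysate aliquot and the plasma all come from the EDTA tube, with no instruction to warm it first, and the spin is 15 minutes at room temperature.

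**The concern.** Until it reaches the laboratory, the tube is protected: the cold chain text in section 8.3 keeps the cold box below 8°C. The lysate procedure ends that protection for the same blood that is about to give the homocysteine result. Staff who follow the SOPs exactly therefore create some of the artefact that the manual warns about.

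Homocysteine is in the primary objective (section 3), and section 4.6 classifies women by a cut-off. Warming can only raise the value, so women are moved across the cut-off in one direction. A confidence interval describes sampling error and does not cover such a shift. Stored plasma cannot be corrected later if nobody recorded how long the blood stood warm.

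**Working it through.** **Order of steps.** Reading section 8.3 with the SOP it refers to, tube 2 goes through: cold box below 8°C; brought to room temperature; remixed; two 100 µL aliquots removed for lysate; remainder spun; plasma frozen. The warming comes before the spin in both folate SOPs.

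**Inputs from the protocol**
- Rate: about 10% per hour at room temperature (section 8.3). This is a statement about the assay and cannot be reproduced from other figures in the plan.
- Cut-off: above 10, printed in nmol/L (Table 3 in section 4.6). The homocysteine SOP gives a normal range of 5–15 µmol/L.
- Planned margin of error: 5 points (section 4.2).

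**Assumptions, none of them in the protocol**
- Avoidable time at room temperature: 15 to 45 minutes. This is a total of 30 to 60 minutes less 15 minutes for the spin, which is needed in any workflow.
- Log-normal values with log-SD 0.3 to 0.4, and true prevalence above the cut-off of 20 to 50%.
- The cut-off read as 10 µmol/L.

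**Concentration.** Measured = true × f, with f = 1 + 0.10 × hours.
- 15 min: f = 1.025, so a true 9.76 µmol/L is read as 10.
- 30 min: f = 1.050, so a true 9.52 is read as 10.
- 45 min: f = 1.075, so a true 9.30 is read as 10.

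**Prevalence.** New prevalence = 1 − Φ(z − ln f / SD), where z is the normal quantile for the true prevalence. Example: true 30%, SD 0.4, 45 min gives z = 0.524 and ln(1.075)/0.4 = 0.181, so 1 − Φ(0.344) = 36.6%, a rise of 6.6 points. The smallest and largest rises over the assumed ranges are:

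| Avoidable time | ln f | Smallest: true 20%, SD 0.4 | Largest: true 50%, SD 0.3 |
|---|---|---|---|
| 15 min | 0.0247 | 21.8% (+1.8) | 53.3% (+3.3) |
| 30 min | 0.0488 | 23.6% (+3.6) | 56.5% (+6.5) |
| 45 min | 0.0723 | 25.4% (+5.4) | 59.5% (+9.5) |

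**Cross-check from the protocol's own range.** Suppose 5–15 µmol/L is the central 95% of a log-normal distribution (an assumption). The geometric mean is √75 = 8.66 and the log-SD is ln 3 / (2 × 1.96) = 0.280.
- Above 10 µmol/L: 30.4% without warming; 33.5%, 36.7% and 39.9% at 15, 30 and 45 min (+3.1, +6.3, +9.5 points).
- Above 15 µmol/L: 2.5% without warming; 3.1%, 3.7% and 4.4% (+0.6, +1.2, +1.9 points).

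**Left out of the sum.** The 30-minute stand in the dark applies to the lysate vial and not to the tube that is spun. The folate SOPs also allow refrigeration before lysis (up to 2 days in one, 4 in the other), which would delay the plasma spin too, but the protocol gives no rate of rise in the cold.

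**The case against.** The strongest reply is that the plan knows about the artefact and limits it. The cold box is kept below 8°C, section 4.5 has specimens processed within 4 hours of collection, section 8.3 has this done the same afternoon, two technicians work on tube 2, and the warning is followed by an instruction to be quick. This stands as mitigation. It does not settle the matter, because being quick and waiting for the tube to reach room temperature pull against each other, and no time limit decides between them.

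The size is also open to challenge. A chilled tube does not rise at the full rate while it is still warming. At 15 minutes the shift is below the planned 5-point margin, and at a cut-off of 15 µmol/L it is small throughout the range shown. All of this is fair, and it is why the figures are illustrations only.

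A reader might infer more than the text supports:
- That high homocysteine will be overstated by a known amount, such as 4 to 13 points. That range needs 30 to 60 minutes at the full rate with the spin counted in, and the protocol states no time.
- That a whole batch is lysed before any tube is spun, so that larger batches are worse. Section 8.3 gives an order of steps but no batch size; about 12 is the number of draws before a transport run.
- That tube 1 already stands at room temperature for the blood count. In the analyzer SOP, room temperature applies to the control material; participant samples are only to be mixed.
- That the prevalence shift applies to the cut-off as printed. Read literally, 10 nmol/L is 0.01 µmol/L, and practically every woman exceeds it with or without warming.

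**Conclusion.** The point holds as a conflict within the laboratory manual that can bias a biomarker of the primary objective in one direction. The order of steps, the warming and the warning are all in the text. The direction, upward, follows from the manual's own statement. The amount does not follow from the documents.

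Under the stated assumptions, the avoidable part is up to about 2.5 to 7.5% in concentration. At a cut-off of 10 µmol/L that means about 2 to 3 percentage points for 15 minutes and about 5 to 10 for 45 minutes, so it can reach or pass the planned margin. It is smaller at a higher cut-off. These figures depend on the assumed times, spread and prevalence, and on how the unit of the cut-off is resolved. The conflict is worth removing before fieldwork because it is avoidable and cannot be undone afterwards.

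**What to change.** Reconcile the processing text, Table 3 and technician tasks in section 8.3, Annexure 2, the two folate SOPs and the separation SOP so that they give one workflow:

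- Take both 100 µL lysate aliquots from tube 1, the blood-count tube. The separation SOP already draws the lysate from the tube used for the blood count, and this also ties the lysate to the hematocrit needed to calculate red-cell folate.
- Keep tube 2 cold, and spin it for plasma on arrival without warming it first. The plasma spin then no longer waits for lysis.
- Record, for each tube 2, the time out of the cold box and the time of the spin. The specimen control form already has fields for temperature and time processed.
- Separately, reconcile the unit of the homocysteine cut-off in Table 3 of section 4.6 with the homocysteine SOP.

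Tubes, staff and volumes drawn stay the same. The cost is edits to the tables, Annexure 2 and task descriptions; lysate making has to be coordinated with the analyzer; and tube 1 has 0.2 of its 3 mL less for reticulocytes and DNA. Any exposure during the spin itself remains.

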Women selected to participate in the sample will be asked to provide informed consent (prior to the blood collection for measurement of biomarkers. For women of reproductive age, blood samples (5-6 mL and 5-6 mL EDTA whole blood) will be collected via venipuncture, and blood tubes will be transported in a cool box to a regional laboratory that will process the specimens within 4 hours of collection.

• Blood collection and processing

Trained phlebotomist will collect 10-12 mL of blood by antecubital venipuncture in certified tubes containing anticoagulant. Due to the nature of the survey, blood samples will be taken in non-fasting conditions. Whole blood with EDTA anticoagulant and non-anti-coagulated whole blood vacutainers well be maintained at 4-8oC for a number of hours and sent to the field laboratory. Upon arrival in the field laboratory whole blood with EDTA anticoagulant will be analyzed by hematology analyzer for determination of hemoglobin and hematocrit. A portion of this blood samples will be separated into serum, plasma, and whole blood and for preparation of aliquots for laboratory processing. A small portion of the EDTA blood will be diluted with ascorbic acid to make red blood cell lysate (1:11 dilution) for determination of RBC folate. The non-anti-coagulated whole blood will be centrifuged after allowing to clot at room temperature for about 30 minutes. After centrifugation, serum will be aliquoted for retinol, Vitamin B12, serum folate, ferritin, soluble transferrin receptor, C - reactive protein, alpha 1 glycoprotein, retinol binding protein. Serum will be then stored at -20oC until shipped to the central lab at TFNC. After samples are received at the central lab, they should be stored at -80 oC until TFNC and/or other labs will conduct biochemical analyses. Detailed procedures for sample collection, shipment, processing and storage are provided in field and laboratory protocol provided in Appendix 8.3.

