- 16. For all participants, fill one yellow top vacutainer with 6 ml of blood and fill 2 Purple Top Vacutainer with 3 ml of blood

Yellow top	Purple top 1	Purple top 2
6 ml	3 ml	3 ml

[figure not shown]
- 17. Upon completion of blood collection, withdraw the needle. Applying heavy pressure as the needle is being withdrawn should be avoided.
- 18. Have the mother/caregiver continue to hold the gauze in place for several minutes. This will help prevent hematomas.
- 19. Invert the Purple Top Vacutainer 10 times after blood collection so that the blood will mix with the EDTA in the tube to prevent clotting. Gently invert the Blue Top Vacutainer 5 times after blood collection to mix with clot activator
- 20. Place an adhesive bandage on the participant's arm
- 21. Label all tubes with the correct and corresponding labels provided (i.e. "Purple Top Vac1" or "Purple top vac 2" or "yellow top vac")
- 22. Place the correct corresponding "Specimen Ctrl" label on the "Biological Specimen Control Form" (Annexure 7) and complete the necessary information
- 23. The needle should be discarded into a sharps container.

- 24. Place **labeled tubes** into a rack inside a cold box with frozen gel packs and discard waste into a biohazard bag.
- 25. Report to the team leader/supervisor any reaction experienced by the participant during the venipuncture procedure

Annexure 7 - Specimen Control Form

BIOLOGICAL SPECIM				HH BIOMA	KKERS CO	DLLECTIC)N			
**Complete all section	is. De sure to sign (.0111/01 10	nn each day							
GENERAL INFORMAT	TION									
District:		Date			I .					
		Date	Day	Month	Ye	ar				
Village:										
Place labels for all wo	men in blocks prov	ided belo	ow Vacutainer (P)	Vac	utainer (P)		Vacutainer (Y)			
Total number of WRA	samples collected			Vac					1	
		- H								
Phlebotomist Name		Phlehot	tomist Signature	•						
SPECIMEN COLLECT		s, AND TI	EMPERATURE	MONITORI	IG FOR CO	JLD BOX				
nstructions for Phleb .) Record the time froze	л	l into the c	old boy in the mo	rning						
2.) Place each WRA's lab					as collected	l and/or te	st was performed	1.		
3.) Record temperature o										
l.) Replace thawing gel µ										
ime frozen gel pack	s placed into the co	old box in	n the morning							
		 							Time	Box #
						nen vials	check (x)	Volume	Processed	
	Specimen T	vpe	NPL- pro	cessing	Serum Fol			-		
					Serum B12	. ,		-		
			CBC		Serum Fer		9	-		
	Vacutainer (P)		WBL		Serum TfR					

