- To ensure proper technique in obtaining quality serum, plasma and hemolysate for laboratory testing is used.
- Ensure high quality serum ,plasma and hemolysate for laboratory testing is obtained
- Ensure proper specimen identification and labeling.
- Ensure separated samples are stored at appropriate temperature.

RESPONSIBILITIES

Laboratory technologist/technicians involved in the study should be trained and follow this SOP during field sample collection and processing at the laboratory.

PROCEDURE

For serum samples:

At local laboratory

- Centrifuge a red top vacutainer tubes that contains clot activator at 1800 RPM for 15 minutes, at room temperature and withdraw all (~ 4ml) serum into a separate labeled cryovial tube.
- > Then, Transport both the clot and sera to regional lab at 4°C

At regional laboratory

- Dispense serum into 325 µl aliquots in labeled tubes with color-coded caps and labels (orange) as indicated: 2 each for serum folate 1 each for ferritin, soluble transferin receptors, retinol, and CRP, 1 extra serum.
- > These volumes are in excess of those required for each determination (250, 200, 300, and 75 μ l, respectively).
- Any additional serum should be saved in more tubes for backup
- > Transfer clot into a smaller labeled 2 ml cryotube
- ➤ All tubes should be logged, placed in storage boxes, and frozen at -70°C.

For Plasma and RBC samples:

At local laboratory

- Mix the EDTA tube again, remove the top of tube, and do CBC using CBC analyzer and record results in the CBC analyzer results form, then transfer remaining blood as follows:
- 100µl transferred into a previously thawed 1ml tube of ascorbic acid (1 g/dL) solution then mix, and allow to stand in the dark 30 min at room temperature (RBC hemolysate),
- then transfer ~ 200 μ l to a separate yellow color-coded whole blood tube.

After removal of the blood aliquots:

- Centrifuge the EDTA tubes at 1800 RPM for 15 minutes at room temperature and withdraw all (~ 2ml) plasma into a separate blue cryovial.
- Then transport whole blood, RBC hemolysate, plasma, and remaining cells in vacutainer to Regional lab at 4°C.

At regional laboratory

- Dispense RBC hemolysate, 4 into aliquots each, containing 275 µl, RBC hemolysate for folate in labeled tubes with color-coded caps and labels.
- Dispense 250 µl of plasma to 2 cryovials each for vitamin B12 and 250 µl of plasma to 2 cryovials each for homocysteine or other analyses including backup of ferritin, retinol, or AGP.

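### The field manual and the separation SOP give incompatible serum procedures (spin, unfrozen transport, freezing point), and nothing says which governs

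*Protocol*

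**What the plan says.** Four parts of the protocol tell staff how to obtain serum.

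- **Section 4.5, blood collection and processing:** "The non-anti-coagulated whole blood will be centrifuged after allowing to clot at room temperature for about 30 minutes". The "serum will be aliquoted for retinol, Vitamin B12, serum folate, ferritin, soluble transferrin receptor, C - reactive protein, alpha 1 glycoprotein, retinol binding protein", which makes eight analytes. Then: "Serum will be then stored at -20oC until shipped to the central lab at TFNC".
- **Appendix 8.3, specimen processing and storage at MPL (field manual):** "For serum separation, the clotted blood sample will be centrifuged at 1000 g for 10 minutes". The serum is then split into four cryovials and a PCR vial and stored at -20°C on site. The tube is the 6 ml yellow top, described under order of draw as the one with gel and clot activator.
- **Annex 6, step 19, repeated in the venous blood SOP:** "Gently invert the Blue Top Vacutainer 5 times after blood collection to mix with clot activator". That SOP fills the yellow top with 4 ml.
- **SOP for sample separation, aliquoting and storage, serum samples:** "Centrifuge a red top vacutainer tubes that contains clot activator at 1800 RPM for 15 minutes, at room temperature". It has staff draw off about 4 ml of serum, then "Transport both the clot and sera to regional lab at 4°C". Aliquots are made and frozen at -70°C only at that regional laboratory.

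**The concern.** The separation SOP is written for this survey by name and requires study staff to be trained in it and to follow it. The field manual is also addressed to the survey's laboratory personnel. Section 4.5 refers readers to Appendix 8.3 for the detail, and that appendix contains both versions without ranking them. A technician therefore has two instructions for spin and transport that cannot both be obeyed.

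Under section 4.5 and the manual, this one tube supplies serum folate, B12, ferritin and soluble transferrin receptor, all named in the primary objective, as well as retinol, RBP, CRP and AGP. Most are reported as prevalences against fixed cut-offs, so an avoidable difference in handling is unwelcome. The folate collection SOP itself treats consistent processing as essential for keeping technique-related variability out of the data.

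**Working it through.** **1. The texts side by side**

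| Item | Section 4.5 | Field manual | Separation SOP |
|---|---|---|---|
| Tube | no colour given | yellow, 6 ml | red |
| Clotting | about 30 min, room temperature | blood called clotted, no time | clot mentioned, no time |
| Spin | not given | 1000 g, 10 min | 1800 RPM, 15 min, no radius |
| After the spin | -20°C until shipped to TFNC | aliquots at -20°C in Morogoro | unfrozen at 4°C to a second laboratory, then -70°C |

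The SOP's unfrozen leg also conflicts with three cold-chain rules in Appendix 8.3. The essentials of cold chain logistics keep processed specimens in a freezer until they go to TFNC. Section 14 moves processed specimens in the portable freezer, apart from one purple-top rack. The notes to Annexure 4 forbid refrigerator storage of processed specimens.

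**2. Is 1800 RPM the same as 1000 g?**

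Relative force = 1.118 × 10⁻⁵ × r (cm) × RPM². With 1800² = 3,240,000 this is 36.22 × r.

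- Radius needed for 1000 g: 1000 / 36.22 = 27.6 cm.
- The documents give no radius, so these are assumptions: 8 cm gives 290 g, 10 cm gives 362 g, 15 cm gives 543 g and 18 cm gives 652 g.
- Force alone is therefore 29% to 65% of the manual's figure over that range.
- Allowing for time: the manual gives 1000 × 10 = 10,000 g-minutes. The SOP gives 290 × 15 = 4,350 to 652 × 15 = 9,780 g-minutes, or 43% to 98%. The longer spin closes part of the gap, and nearly all of it at the largest radius.

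**3. Can the SOP's serum yield occur?**

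Ceiling = fill volume × (1 − Hct). The protocol's own default Hct, in the RBC folate calculation, is 40%.

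- 4 ml fill (venous blood SOP): 4 × 0.60 = 2.4 ml.
- 6 ml fill (field manual): 6 × 0.60 = 3.6 ml.
- To get 4 ml from a 6 ml fill, Hct must be 1 − 4/6 = 33%, with complete recovery.

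The stated 4 ml is impossible from the smaller fill and slightly too high for the larger.

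**4. Is there enough serum for the aliquots?**

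- Field manual: 4 × 300 + 100 = 1,300 µl.
- Separation SOP: two folate tubes, one each for ferritin, transferrin receptor, retinol and CRP, and one extra: 7 × 325 = 2,275 µl.

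Both fit within 2.4 ml, but the SOP needs 2,275 / 2,400 = 95% of the ceiling.

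**The case against.** Much of the disagreement can be read as careless wording, and several stronger inferences fail.

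- **That one version spins unclotted blood.** It does not. The manual speaks of a clotted sample and the SOP handles the clot. Only the time and temperature are missing outside section 4.5.
- **That three different tubes are in use, or that the yellow tube goes unmixed.** Annexure 3 supplies only yellow and purple tubes, and yellow is the one with clot activator, so blue and red are naming slips. Step 4 of the manual's venous blood collection list tells staff to mix the specimens, without restriction by colour.
- **That women will be lost, or results will differ, by crew or enumeration area.** The manual places serum processing in one laboratory and gives the serum spin to one technician, so a choice between the texts could well apply uniformly. The aliquot volumes also fit the smaller fill.
- **That all eight analytes are exposed under either text.** The separation SOP names serum tubes only for folate, ferritin, transferrin receptor, retinol and CRP, and puts B12 in plasma.
- **That the SOP's spin is inadequate.** No minimum force is documented, the radius is unknown, and the longer time compensates in part.

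Training and a field pilot are planned, but section 4.5 does not say which procedure will be taught. What survives is the direct conflict on spin, on unfrozen transport and on where and how cold serum is frozen, together with the unstated clotting time, the tube names and the impossible yield.

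**Conclusion.** The point stands as an inconsistency between two operative procedures, and it should be corrected before fieldwork. The spin settings differ unless the rotor radius is near 27.6 cm; the 290 to 650 g range rests on assumed radii of 8 to 18 cm. The transport and freezing steps differ without any assumption. The 4 ml yield exceeds the ceiling by 1.6 ml for the 4 ml fill and by 0.4 ml for the 6 ml fill, at the protocol's default haematocrit of 40%.

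A reader might infer biased prevalence estimates or differential loss of samples. The documents contain nothing from which either could be calculated, so any such effect is plausible but not shown. Nor do they settle which version is right.

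**What to change.** Reconcile section 4.5, the manual's processing and aliquoting text, Annex 6, the venous blood SOP and the separation SOP into one serum procedure that states:

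- one tube name, matching the supply list, and one fill volume;
- one clotting time and temperature before the spin;
- one spin in g and minutes, with the RPM worked out for the survey centrifuge;
- one statement of where serum is aliquoted and frozen, and at what temperature, consistent with the cold-chain essentials, section 14 and Annexure 4.

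Correct the 4 ml yield, and state that this procedure replaces the others. The cost is editing plus one RPM conversion. Section 4.5 already plans for the clotting period, so stating it elsewhere adds no new step.
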